6.4. Examples of participant feedback

Below are some examples of the types of feedback that are being considered:

- (a) Questionnaire insights are under development and may include comparisons to healthy recommendations, comparisons to the population, as well as resources participants may wish to consult.
- (b) Baseline physical measurements (blood pressure, height, weight, waist circumference) as well as baseline blood measures of cholesterol. These measurements are not intended to be a 'health check' and are not, for now, shared with their GP or the NHS. However, we are working with the NHS and the Office for Health Improvement and Disparities to explore potential options for sharing these data with the NHS in the future. We will provide written feedback to participants about their blood pressure, heart rate, and cholesterol (from a POCT/ 'finger-prick' test) on a proforma with advice to contact NHS 111, a Pharmacist or GP in the rare circumstances where that is necessary or if they have e(i.e measurements that warrant medical attention immediately or within days e.g. a very low heart rate). For the vast majority of results, we will also direct participants to the NHS website on blood pressure, and the British Heart Foundation website on cholesterol where they can obtain further information and advice.
- (c) Being approached by NHSBT if their genotypes suggest that they have less common minor blood group antigens that are underrepresented among NHSBT blood donors. This may be particularly beneficial for minority groups for whom NHSBT sometimes has difficulty providing optimally matched blood products.
- (d) Providing participants with increased access to information stored in their NHS health care records.
- (e) Integrated risk scores that provide disease risk estimates. Leading integrated risk score candidates that may initially be feedback to participants include cardiovascular disease,⁶² age-related macular degeneration, glaucoma, and type II diabetes. Each of these integrated risk scores provides good risk prediction and are clinically actionable.
- (f) Other examples include risk predictions based on common genetic variants associated with risk of iron overload, deep venous thrombosis, or that influence the efficacy or side effects of prescription drugs.

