- 3 Someone of the opposite sex
- 4 Someone of the same sex
- 4 Other
- 3 Prefer not to answer

→ GO TO D4

[MARITAL_STATUS_D (CENSUS 2021)]

Who was your registered civil partnership to?

SELECT 1 from

- 5 Someone of the opposite sex
- 6 Someone of the same sex
- 5 Other
- 3 Prefer not to answer

→ GO TO D4

[D4 (UKB)]

What type of accommodation do you live in?

SELECT one of 7 from

- 1 A house or bungalow
- 2 A flat, maisonette or apartment
- 3 Mobile or temporary structure (i.e. caravan)
- 4 Sheltered accommodation **-> GO TO D5A**
- 5 Care home **-> GO TO D5A**
- 7 None of the above
- 3 Prefer not to answer

Please select:

-A house or bungalow for any whole, detached, semi-detached or terraced (including end-terrace) house or bungalow.

-A flat, maisonette, or apartment for any purpose-built block of flats or tenement, part of a converted or shared house (including bed-sits) or within a commercial building (for example in an office building, or hotel, or over a shop).

-If none of the options apply, select 'None of the above'.

[D5 (UKB)]

Do you own or rent the accommodation that you live in?

SELECT one of 8 from

- 1 Own outright (by you or someone in your household)
- 2 Own with a mortgage
- 3 Rent - from local authority, local council, housing association, student accommodation
- 4 Rent - from private landlord or letting agency
- 5 Pay part rent and part mortgage (shared ownership)
- 6 Live in accommodation rent free
- 7 None of the above

-3 Prefer not to answer

Please select:

- Own outright if you or someone in your household owns the accommodation that you live in.
- Own with mortgage if you or someone in your household has a mortgage on the accommodation that you live in.

[D5A (UKB)]

Do you have any of the following in your home? (You can select more than one answer)

TOGGLE of 6 choices

[Require >1 response]

- 1 A gas hob or gas cooker
- 2 A gas fire that you use regularly in wintertime
- 3 An open solid fuel fire that you use regularly in wintertime
- 7 None of the above **[EXCLUSIVE]**
- 1 Do not know **[EXCLUSIVE]**
- 3 Prefer not to answer **[EXCLUSIVE]**

Select the answer which best describes how your home is mainly heated. If you use more than one type of heating equally, you can choose multiple answers. Solid fuel refers to wood or coal. Regular use is when you use this for most days of the week in the winter time.

[D5A1 (UKB)]

How many years have you lived at your current address?

Enter INTEGER

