[D2A (UKB)]

What year did you first come to live in the United Kingdom?

Please enter a date in the following format: dd/mm/yyyy

Enter INTEGER

OR

- 1 Do not know

OR

- 3 Prefer not to answer

Please give the year that you FIRST came to live in the United Kingdom. Do not count years if you came to holiday or visit friends or family.

[Y1 (UKB)]

Were you adopted as a child?

SELECT one of 4 from

- | | |
|----|-------------|
| 1 | Yes |
| 0 | No |
| -1 | Do not know |

-3 Prefer not to answer

[Y13 (UKB)]

Is your biological father still alive?

SELECT one of 4 from

1 Yes

0 No

-> GO TO Y13B (UKB)

-1 Do not know

-> GO TO Y13D (UKB)

-3 Prefer not to answer

-> GO TO Y13D (UKB)

[Y13A (UKB)]

What is his age now?

Enter INTEGER

[Require > current age, ≤ 122

Units: years]

OR

-1 Do not know

OR

-3 Prefer not to answer

[Y13B (UKB)]

What was his age when he died?

Enter INTEGER

[Require ≥ 10, ≤ 122

Units: years]

OR

-1 Do not know

OR

-3 Prefer not to answer

[Y13D (UKB)]

Has/did your biological father ever suffer from?

You can select more than one answer

We will ask more details for any type of disorder that you select here

TOGGLE

[Require ≥1 choices]

0 Autoimmune disorder -> GO TO AUTO_A

1 Blood disorders (Anaemia) -> GO TO BLOOD_A

2 Cancer -> GO TO CANC_A

- 4 Digestive system or liver problems -> **GO TO DIG_A**
- 5 Endocrine, nutritional and metabolic disorders (e.g., diabetes, thyroid disorder, vitamin deficiencies) -> **GO TO EN_A**
- 6 Eye or visual problems -> **GO TO EYE_A**
- 7 Fractures, breaks, or joint problems -> **GO TO FRAC_A**
- 8 Heart or circulatory disease (e.g., high blood pressure or stroke) -> **GO TO HEART_A**
- 9 Kidney or urinary system disorders -> **GO TO KIDN_A**
- 10 Lung or respiratory problems -> **GO TO LUNG_A**
- 11 Mental health conditions (e.g. depression, bipolar disorder) -> **GO TO MH_A**
- 12 Neurodevelopmental conditions (e.g., Autism spectrum disorder, ADHD) -> **GO TO ND_A**
- 13 Neurological disorders (things that affect that brain or nervous system) -> **GO TO NEU_A**
- 14 Reproductive system problems -> **GO TO REPRO_A**
- 15 Other not listed -> **GO TO Y16 (UKB)]**
- 16 None of these -> **GO TO Y16 (UKB)]**
- 1 I don't know **[EXCLUSIVE]** -> **GO TO Y16 (UKB)]**
- 3 Prefer not to answer **[EXCLUSIVE]** -> **GO TO Y16 (UKB)]**

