- 2 Enlarged prostate
- 3 Fibrocystic Breast, or another Benign Breast Disease (such as proliferative Benign Breast Disease or LCIS)
- 4 Ductal Carcinoma in situ (DCIS)
- 5 Uterine Fibroids
- 6 Other (not listed)

- 1 I don't know
- 3 Prefer not to answer

[Y16 (UKB)]

Is your biological mother still alive?

SELECT one of 4 from

- 1 Yes
- 0 No -> GO TO Y16B (UKB)
- 1 Do not know -> GO TO Y16D (UKB)
- 3 Prefer not to answer -> GO TO Y16D (UKB)

[Y16A (UKB)]

What is her age now?

Enter INTEGER

[Require > current age, ≤ 122

Units: years]

OR

- 1 Do not know

OR

- 3 Prefer not to answer

[Y16B (UKB)]

What was her age when she died?

Enter INTEGER

[Require > current age, ≤ 122

Units: years]

OR

- 1 Do not know

OR

- 3 Prefer not to answer

[Y16D (UKB)]

Has/did your mother ever suffer from? (You can select more than one answer)

TOGGLE

[Require ≥1 choices]

- 2 Autoimmune disorder -> GO TO AUTO_A
- 3 Blood disorders (Anaemia) -> GO TO BLOOD_A
- 2 Cancer -> GO TO CANC_A
- 3 Complications or difficulties in pregnancy or childbirth -> GO TO PREG_A
- 4 Digestive system or liver problems -> GO TO DIG_A

- 5 Endocrine, nutritional and metabolic disorders (e.g., diabetes, thyroid disorder, vitamin deficiencies) -> **GO TO EN_A**
- 6 Eye or visual problems -> **GO TO EYE_A**
- 7 Fractures, breaks, or joint problems -> **GO TO FRAC_A**
- 8 Heart or circulatory disease (e.g. high blood pressure or stroke) -> **GO TO HEART_A**
- 9 Kidney or urinary system disorders -> **GO TO KIDN_A**
- 10 Lung or respiratory problems -> **GO TO LUNG_A**
- 11 Mental health conditions (e.g.depression, bipolar disorder) -> **GO TO MH_A**
- 12 Neurodevelopmental conditions (e.g., Autism spectrum disorder, ADHD) -> **GO TO ND_A**
- 13 Neurological disorders (things that affect that brain or nervous system) -> **GO TO NEU_A**
- 14 Reproductive system problems -> **GO TO REPRO_A**
- 15 Other not listed -> **GO TO Y17 (UKB)]**
- 16 None of these -> **GO TO Y17 (UKB)]**
- 1 I don't know [**EXCLUSIVE**] -> **GO TO Y17 (UKB)]**
- 3 Prefer not to answer [**EXCLUSIVE**] -> **GO TO Y17 (UKB)]**

Answer this question for blood relations only. If you are not sure if your mother suffered from any of the listed illnesses, please select 'Do not know'. If you know your mother suffered from certain listed illnesses but are unsure about others, only select the ones you are sure about.

[AUTO_A_MOM]

Has your mother ever been diagnosed with any of the following autoimmune disorders?

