- OR**
- 4 Do not remember
- OR**
- 3 Prefer not to answer

[FH3D (UKB)MM]

How old were you when you had your LAST child?

- Enter INTEGER**
[Require ≥ 8 , \leq current age
Units: years]
- OR**
- 4 Do not remember
- OR**
- 3 Prefer not to answer
-
- ➔ IF SEX = Male GO TO L1 (UKB)
 - ➔ IF SEX = Prefer not to answer GO TO FH7 (UKB)

[FH7 (UKB)]

Have you ever been for breast cancer screening (a mammogram)?

- SELECT one of 4 from**
- 1 Yes
 - 0 No -> FH8
 - 1 Do not know -> FH8
 - 3 Prefer not to answer -> FH8

[FH7A (UKB)]

How many years ago was your last screen?

Enter INTEGER

[Require ≥ 0 , \leq current age]

OR

-10 Less than 1 year ago

OR

-1 Do not know

OR

-3 Prefer not to answer

If you are unsure, please provide an estimate or select 'Do not know'.

[FH8 (UKB)]

Have you ever had a cervical smear test?

SELECT one of 4 from

1 Yes

0 No -> FH1

-1 Do not know -> FH1

-3 Prefer not to answer -> FH1

[FH8B (UKB)]

How many years ago was your last cervical smear test?

Enter INTEGER

[Require \geq current age]

OR

-10 Less than a year ago

OR

-1 Do not know

OR

-3 Prefer not to answer

If you are unsure, please provide an estimate or select 'Do not know'.

[FH1 (UKB)]

How old were you when your periods started?

Enter INTEGER

[Require ≥ 5 , \leq current age]

Units: years]

OR

-1 Do not know

OR

-3 Prefer not to answer

If you are unsure, please provide an estimate or select 'Do not know'.

[FH2 (UKB)]

Have you had your menopause (periods stopped for more than 12 months)?

SELECT one of 5 from

- | | | |
|----|-------------------------------|---------------|
| 1 | Yes | -> FH2A (UKB) |
| 0 | No | -> FH2B (UKB) |
| 2 | Not sure - had a hysterectomy | |
| 3 | Not sure - other reason | -> FH2B (UKB) |
| -3 | Prefer not to answer | |

➔ IF (ANSWER = 2 OR ANSWER = -3) AND MH7 > 0 GO TO FH5 (UKB)

➔ IF (ANSWER = 2 OR ANSWER = -3) AND MH7 < 0 GO TO FH3 (UKB)

[FH2A (UKB)]

How old were you when you had your last period?

Enter INTEGER

[Require \geq FH1 integer, \leq current age]

OR

-1 Do not know

OR

-3 Prefer not to answer

➔ IF MH7 > 0 GO TO FH5 (UKB)

➔ ELSE GO TO FH3

If you are unsure, please provide an estimate or select 'Do not know'.

[FH2B (UKB)]

How many days since your last menstrual period?

Enter INTEGER

[Require \geq 0, \leq 365,

Units: days]

OR

-10 **More than one year**

OR

-1 Do not know

OR

-3 Prefer not to answer

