If you are currently taking the pill, select 'Still taking the pill'. If you are unsure, please provide an estimate or select 'Do not know'.

[FH6 (UKB)]

Have you **ever** used hormone replacement therapy (HRT)?

SELECT one of 4 from

1 Yes

0 No -> **GO TO FH9**

-1 Do not know -> **GO TO FH9**

-3 Prefer not to answer -> **GO TO FH9**

[FH6A (UKB)]

How old were you when you first used HRT?

Enter INTEGER

[Require \geq 16, \leq current age]

OR

-1 Do not know

OR

-3 Prefer not to answer

If you are unsure, please provide an estimate or select 'Do not know'.

[FH6B (UKB)]

How old were you when you last used HRT?

Enter INTEGER

[Require \geq FH6A, \leq current age]

OR

-1 Do not know

OR

-11 Still taking HRT

OR

-3 Prefer not to answer

If you are currently using HRT, select 'Still taking HRT'.

If you are unsure, please provide an estimate or select 'Do not know'.

[FH9 (UKB)]

Have you had a hysterectomy (womb removed)?

SELECT one of 4 from

1 Yes

0 No -> GO TO FH10

-5 Not sure -> GO TO FH10

-3 Prefer not to answer -> GO TO FH1

[FH9A (UKB)]

How old were you when you had your hysterectomy?

Enter INTEGER

[Require \geq 0, \leq current age]

OR

-1 Do not know

OR

-3 Prefer not to answer

If you are unsure, please provide an estimate or select 'Do not know'.

[FH10 (UKB)]

Have you had BOTH ovaries removed?

SELECT one of 4 from

1 Yes

0 No -> GO TO L1(UKB)

-5 Not sure -> GO TO L1(UKB)

-3 Prefer not to answer -> GO TO L1(UKB)

Only enter 'Yes' if you have had both ovaries removed

If you are unsure of whether both ovaries have been removed, select 'Do not know'.

[FH10A (UKB)]

How old were you when you had BOTH ovaries removed?

Enter INTEGER

[Require ≥ 0 , \leq current age]

OR

-1 Do not know

OR

-3 Prefer not to answer

[L1 (UKB)]

Have you ever been diagnosed with any of the following by a doctor or other health professional?

Please select all that apply

We will ask more details for any type of disorder that you select here

TOGGLE

[Require ≥ 1 choices]

- 6 Autoimmune disorder -> **GO TO AUTO_A**
- 7 Blood disorders (Anaemia) -> **GO TO BLOOD_A**
- 2 Cancer -> **GO TO CANC_A**
- 3 Complications or difficulties in pregnancy or childbirth -> **SHOW IF FEMALE; GO TO PREG_A**
- 4 Digestive system or liver problems -> **GO TO DIG_A**
- 5 Endocrine, nutritional and metabolic disorders (e.g., diabetes, thyroid disorder, vitamin deficiencies) -> **GO TO EN_A**
- 6 Eye or visual problems -> **GO TO EYE_A**

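### Two hard range checks in the baseline questionnaire, on mother's age at death and years since last smear, reject true answers as written

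*Protocol*

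**What the plan says.** Section 3.6 of the Protocol presents Appendix E as the improved baseline questionnaire, reviewed by the Scientific Advisory Board after the pilots. It is therefore the current instrument.

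- **Y16B** (Appendix E, Section 4) asks "What was her age when she died" and carries the check "Require > current age, ≤ 122". Y13A and Y16A, on the present age of a living father or mother, have the same check.
- **Y13B**, the father's age at death, carries "Require ≥ 10, ≤ 122".
- **FH8B** (Section 5) asks "How many years ago was your last cervical smear test" and carries "Require \geq current age", that is, at least current age. The parallel items FH7A (mammogram), MH3 (PSA) and H10A (bowel screening) run from 0 to current age.
- **D5A** (Section 1, heating and cooking appliances) carries "Require >1 response", although its none, don't-know and decline options are each marked exclusive.
- **Response numbers** repeat within several lists. In L1, for example, "6 Autoimmune disorder" stands in the same list as eye problems, also numbered 6.

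D11 lists a Require rule and a separate Expect rule, so Require reads as a hard check and not a warning.

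**The concern.** A hard check that rejects a true answer leaves the participant three ways out: don't know, decline, or a false value that passes. None can be undone at analysis.

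For Y16B the loss depends on the value being measured. Early maternal deaths are the ones rejected, more often the older the participant, and the father's item has no such restriction. Take a 60-year-old whose parents both died at 58: the father's age is accepted and the mother's is refused. Recorded maternal ages at death would be truncated from below at the participant's own age, and a comparison of maternal with paternal longevity would be distorted. The linkage in Section 5 concerns participants' own records, and the Protocol describes no other source for a mother's age at death.

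For FH8B, the time since last cervical screening would be missing or false for almost everyone not screened within the past year.

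**Working it through.** The plan states no figure here to reproduce. The check sets parallel items side by side and then illustrates the size of the Y16B loss.

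**1. Range rules compared**

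| Quantity | Item | Accepted range |
|---|---|---|
| Father's age now | Y13A | above participant's age, up to 122 |
| Father's age at death | Y13B | 10 to 122 |
| Mother's age now | Y16A | above participant's age, up to 122 |
| Mother's age at death | Y16B | above participant's age, up to 122 |
| Years since mammogram | FH7A | 0 to current age |
| Years since smear | FH8B | at least current age |

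A living parent must be older than the participant, so the rule is right in Y13A and Y16A. A dead parent need not have reached the participant's present age, so it is wrong in Y16B.

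**2. FH8B.** Let a be current age and y the whole years since the test. A true answer of one year or more satisfies 1 ≤ y ≤ a − 1; the rule demands y ≥ a. The two cannot both hold. Over all pairs with a from 18 to 99, the number accepted is 0. A 40-year-old may enter only 40 or more, so every answer from 1 to 39 is refused. Only the code for under a year, don't know and decline remain.

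**3. Y16B, illustrative size.** Let a be the participant's age, m the mother's age at the birth and D her age at death. A deceased mother has m < D < a + m, and the rule rejects D ≤ a. The rejected share is

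P(D ≤ a | m < D < a + m) = [F(a) − F(m)] / [F(a + m) − F(m)].

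The documents give no distribution for D. The following are assumptions: D normal with mean/SD 75/15, 78/14 or 82/12, and m = 25 or 30. For 78/14, m = 25, a = 60: F(60) = Φ(−1.286) = 0.099, F(85) = Φ(0.5) = 0.691 and F(25) ≈ 0, so the share is 0.099/0.691 = 0.14.

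| Participant's age | 75/15 (m = 25, 30) | 78/14 (m = 25, 30) | 82/12 (m = 25, 30) |
|---|---|---|---|
| 50 | 0.09, 0.07 | 0.05, 0.04 | 0.01, 0.01 |
| 60 | 0.21, 0.19 | 0.14, 0.12 | 0.06, 0.04 |
| 70 | 0.41, 0.39 | 0.32, 0.30 | 0.18, 0.17 |
| 80 | 0.65, 0.64 | 0.57, 0.56 | 0.45, 0.44 |

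With the Y13B range, no true age at death from 10 to 122 is refused.

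**4. D5A.** An exclusive option is a single response, and a single response fails a rule of more than one. Read literally, anyone with no appliance or one appliance has no valid answer.

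**5. Repeated numbers** (between positive codes; the extracted text blurs minus signs)

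- EYE_A: glaucoma shares 1 with visual impairment (mother), 2 with double vision (sibling) and 3 with night blindness (self). The father's list is clean.
- DIG_A: 5 is ulcerative colitis and other. EN_A: 3 is underactive thyroid and other. Both occur in all four versions.
- Y16D: 2 is autoimmune and cancer; 3 is blood and pregnancy. Y19: 4 is autoimmune and digestive; 5 is blood and endocrine. L1: 6 is autoimmune and eye; 7 is blood and fractures.

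**The case against.** The strongest reply concerns the codes. A reader might infer that the repeated numbers merge diseases in the data beyond recovery. The documents do not support that. Much of the numbering looks like a word processor's list counter running on: hip fracture is 0, 15, 30 and 45 across father, mother, sibling and self, and glaucoma is 0, 1, 2 and 3. The key to Appendix E does not say that printed numbers are stored values, and Section 9.6 treats data dictionaries separately. In L1, Y16D and Y19 each option leads to its own follow-up, so those collisions can be resolved. Participants' own diagnoses are also sought through linked records. What stands is narrower: the leaf lists (EYE_A, DIG_A, EN_A) have no follow-up that separates the answers, and some routing rules do use printed numbers (for example WP1 = -2), so confirmation is reasonable.

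Nor do the documents show harm to risk scores. Section 6.4 names "age-related macular degeneration, glaucoma, and type II diabetes" among scores that may be fed back, but nothing says a score uses the EYE_A code.

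D5A is probably a one-symbol slip, since nearly all other multiple-choice items ask for at least one response. Section 3.6 reports that 95% of pilot participants who started the questionnaire finished it, which would be hard to reach with a literal D5A rule. The pilots used an earlier questionnaire, though, and it is not shown that D5A was unchanged.

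FH8B also turns on few symbols, so its printed rule should be checked in the source file. Y16B does not: the whole rule matches the living-mother item.

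**Conclusion.** Y16B and FH8B are wrong as written. Each contradicts its parallel item, and nothing elsewhere in the Protocol corrects them. If built as printed, FH8B accepts no true interval of one year or more, and Y16B rejects every true age at death at or below the participant's age. The Y16B share is small in younger participants and grows with age, to roughly 4–21% of deceased mothers at participant age 60 and 17–41% at 70. Those figures rest wholly on assumed mortality and maternal age.

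Two stronger readings should be resisted. From Table 1, 682,122 + 446,610 + 150,031 + 139,227 = 1,417,990 participants would be 60 or over, 28.4% of 5 million. That is not the share of answers lost, because it includes people whose mother is alive or died at a greater age than theirs. Nor are all early maternal deaths removed: a 35-year-old can still record a mother who died at 45, and Y16D still collects the mother's diseases. Permanent loss is a fair description for mother's age at death and, only if the printed codes are stored, for relatives' leaf-level diagnoses.

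**What to change.** - Y16B: accept 10 to 122, as in Y13B.
- FH8B: accept 0 to current age, as in FH7A.
- D5A: require at least one response.
- Before deployment, give each option in EYE_A, DIG_A, EN_A, Y16D, Y19 and L1 a unique code, preferably the same for self, mother, father and sibling, and confirm in the data dictionary which values are stored.

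The cost is an edit to the questionnaire specification using rules already in Appendix E, with no added participant burden. If any data have been collected under the printed checks, the rejected answers can be restored only by asking again.
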